6.2 Study drug accountability

The Sponsor will supply sufficient quantities of the study drug for the completion of this study. The study pharmacist or designated study personnel will maintain a Drug Application Log. All product bottles must be accounted for, and any discrepancies explained. Study site should contact site Clinical Research Associate (CRA) in case of any dispensing errors or if discrepancies are discovered.

At the end of the study, the Investigator will retain all the original documentation regarding study drug accountability, return, and copies will be sent to the Sponsor. All unused and used Study Drug bottle will be returned to the Sponsor or its designee for destruction at the end of the study. Retention is stored on site with Sponsor instructions.

7. Study procedures and schedule of events

7.1 Study procedures and evaluations

Informed Consent, Eligibility Criteria, Subject Demographics, hair type and Investigational Product Dispensation/ Application on Day 0.

Medical History, Vital signs, Physical Examination, Head Lice Visual Assessment, Local Skin/Scalp Irritation Assessment, Ocular Irritation Assessment and Adverse Events Assessment will be collected at Baseline Visit 1 (post treatment), Visit 2, visit 3 and Final Study Visit 4.

Basic demographic information, including date of birth, sex, ethnicity, and race will be recorded at the Screening /Baseline Visits. Relevant medical history, and past history of head lice will be documented. All medications (both prescription and

nonprescription), including vitamins, herbals, topical, inhaled, and intranasal taken within 30 days prior to the start of the Study Drug and through the final study visit will be recorded on the appropriate source document (using their generic and/or brand names), if known with the corresponding indication, start and stop dates. At each study visit, subjects will be asked whether they have started or discontinued any medication since their previous study visit. This includes single use or PRN (as needed medication use).

Vital signs will include body temperature, heart rate and blood pressure (systolic and diastolic). Blood pressure and pulse rate will be measured after the subject has been sitting restfully for at least 5 minutes. Any abnormal characteristics of vital signs will be evaluated by the Investigator based on their significance. Any abnormal vital signs will be considered AEs if they require therapeutic medical intervention, and/or if the Investigator considers them to be AEs based on his/her clinical judgement.

Physical examination, including height, weight, and evaluation of organs and systems (General Appearance, Heart/Cardiovascular, Lungs, Gastrointestinal, Ears / Nose / Throat, Extremities, and Skin) will be assessed at Visit 1 Day 0, Visit Day 2, Visit Day 7, and Final Study Visit Day 14

Urine Pregnancy Test and Concomitant/ Prohibited Medication Review will be performed on all Visits.

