4.1 Description of the Study Design

This is a Study to Evaluate the Safety and Efficacy of Alliance Pharmaceutical Product in Subjects Infested with Pediculosis Capitis. The subject population includes healthy male and female subjects aged 2 years and up who are infested with *Pediculus humanus capitinis*. Household members infestation with an active head lice, defined as at least 1 live louse (adult and/or nymph) present on the scalp and/or hair as determined by a trained evaluator, will receive treatment with study product at baseline.

The planned overall sample size for this clinical trial is approximately n=58 subjects, equally divided between treatment and control groups. Potential subjects will be screened for eligibility and if eligible to participate, their infestation level will be rated. Eligible subjects at each infestation level will be assigned alternately to the treatment or control group to ensure that the two groups have approximately equal representations of infestation severity levels. Level of infestation will be rated as heavy, moderate or light described by how quickly lice were found during combing: heavy infestation = >1 louse with one stroke of the comb; moderate infestation = 1 louse with one stroke of the comb; light infestation = first louse found only after several strokes of the comb

After assignment to a study group, each eligible subject will receive the application of either the Alliance Pharmaceutical Product Vamousse Spray 'n' Go drug or the Permethrin-based control drug. Infested household members will be treated with the Vamousse Spray 'n' Go or Permethrin lotion on-site (i.e., the household members should be assigned to the same treatment as the index case). During the baseline visit (Day 0), the Investigator and clinical staff members will record subject's demographics; elicit informed consent; obtain medical history; review concomitant medication to identify any prohibited therapies the subject may be receiving; collect vital signs; conduct visual assessment of head lice, specifically counting live lice and nits with stages noted, using a 15 inch led 5x magnifying procedure lamp and if needed for confirmation, laboratory microscopes; perform physical examination; assess local skin/ scalp irritation; assess ocular irritation; perform urine pregnancy test on females; and conduct an adverse event assessment.

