7.3 Study schedule

7.3.1 Screening/randomization

Screening Visit Day 0 (Visit 1)

- Obtain informed consent of potential participant verified by signature on written informed consent.
- Record demographic information, obtain medical history, and history of head lice.
- Review medications history and concomitant/prohibited medications to determine eligibility
- Verify inclusion/exclusion criteria.
- Collect urine sample for pregnancy testing for all subjects of childbearing potential.
- Perform assessment for living head lice on subjects and household members for a minimum of 15 minutes. Each subject must have at least 1 live louse. Rate severity of infestation. After each subject has been identified, additional infested household members will also be assessed for infestation.
- Level of infestation will be rated as heavy, moderate or light described by how quickly lice were found during combing: heavy infestation = >1 louse with one stroke of the comb; moderate infestation = 1 louse with one stroke of the comb; light infestation = first louse found only after several strokes of the comb
- Household members must have an active head lice infestation defined as: At least 1 live lice (adult and/or nymph) present on the scalp and/or hair, as determined by a trained evaluator. Household members will be assigned to the same study group as index case.
- Schedule study visits for participants who are eligible and available for the duration of the study.
- Randomly assign subjects to treatment or control group based on infestation severity alternation system (i.e., randomly assign pairs of equal severity levels to treatment and control groups, a form of stratified random sampling) to achieve balanced representation of severity in the two groups.
- Investigational Product Dispensation/ Application for subject.
- Provide each subject with homecare instructions including combing after first wash out.
- Inform subject when to come back for each follow-up visit.
- Provide Standard of Care treatment on-site to unqualified infested household members.

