10.4.2 Assessment of primary and secondary endpoints

Primary Outcome:

To test the hypotheses for this outcome for each of the two endpoints, the counts of subjects in the treatment and control groups who were lice free at each endpoint will be converted into proportions of the respective group. These proportions along with the group sample sizes will be used to compute the necessary Z statistics for independent proportions.

Secondary Outcome:

To test the hypotheses for this outcome for each of the two endpoints, the difference between the day 14 and baseline counts of live lice (i.e., total of live adult lice and nymphs) will be computed for each participant. The mean difference in counts for the treatment and control groups will be tested using the t-test for independent means.

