10.5 Sample Size

Sample size is 52. The requisite sample size for the *t*-test of the means of independent samples, assuming a Cohen's *d* of .40, alpha .05 two-tailed, and a power of .80, was smaller at 44. Thus, the larger requisite sample size for the *z*-test will also suffice for the *t*-test and will provide a cushion for the application of the Holm correction for Type I error. The sample size of 52 should be increased to account for a 10% expected dropout rate, resulting in a total sample size, rounded to an even number, of 58 (26 per group).

Expected difference:

40% difference between treatment groups, based on results of LiceFreee Spray (1% Sodium Chloride) compared to Permethrin; the results showed significantly higher pediculicidal activity for Sodium Chloride spray (85%) as compared to Permethrin (45%) at Day 15 ($p < 0.05$)¹.

A pilot study using Vamousse Spray 'n' Go as a once only treatment, showed high early lice kill (88% lice free at day 0 after treatment) but low efficacy at day 14 (12% lice free). It is anticipated that repeat dosing after 7 days, if live lice are present, will boost day 14 efficacy to levels similar to those at day 0.

Assumptions:

80% power, 0.05 alpha
Allocation ratio 1:1

Methods:

Calculations performed in Stata/IC 16.1
Binary data (lice free – Y/N) – proportions
Independent samples
Chi Squared, two-sided test

Sample:

Estimated sample sizes for a two-sample proportions test
Pearson's chi-squared test
 $H_0: p_2 = p_1$ versus $H_a: p_2 \neq p_1$
Study parameters:

```
alpha = 0.0500
power = 0.8000
delta = 0.4000 (difference)
p1 = 0.4500
p2 = 0.8500
```

Estimated sample sizes:

$N = 52$
 N per group = 26
Allowance for drop out: 10% per group, 3
Total sample: 29 per group (58)

References:

¹ Serrano, L. et al. Evaluation of the Efficacy and Safety of 1% Sodium Chloride (LiceFreee Spray) against 1% Permethrin Crème Rinse on Head Lice Infested Individuals. *Pharmacology & Pharmacy*, 2013, 4, 266-273.

11 Source documents and access to source data/documents

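### Section 7.1 times the Day 0 louse assessment after treatment, and no section says that the baseline live-louse count precedes the first application

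*Combined protocol and SAP*

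**What the plan says.** Section 7.1 groups seven procedures (medical history, vital signs, physical examination, Head Lice Visual Assessment, skin/scalp irritation, ocular irritation and adverse events) and states that they "will be collected at Baseline Visit 1 (post treatment), Visit 2, visit 3 and Final Study Visit 4".

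Section 7.3.1 gives a different order for the same day. Its list has staff "Perform assessment for living head lice on subjects and household members for a minimum of 15 minutes", followed by "Each subject must have at least 1 live louse. Rate severity of infestation". Assignment comes later in the list, and after that "Investigational Product Dispensation/ Application for subject". Section 4.1 agrees on this order: "Potential subjects will be screened for eligibility and if eligible to participate, their infestation level will be rated", then assignment, then application.

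The only description of a Day 0 count is in 4.1, where staff are to "conduct visual assessment of head lice, specifically counting live lice and nits with stages noted". That sentence follows the one on application and is timed only to the Day 0 visit. The schedule of events (16.1) marks one Head Lice Visual Assessment on Day 0, with no timing relative to application.

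Section 10.4.2 bases the secondary outcome on "the difference between the day 14 and baseline counts of live lice", compared between arms by a t-test. Section 10.3 states that hypothesis for Day 14 and a parallel one for Day 7. Neither section says which Day 0 count is the baseline.

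**The concern.** A change-from-baseline analysis needs a baseline that treatment has not touched. Section 7.1 is the only place that gives the named Day 0 louse assessment an explicit time relative to application, and the time it gives is after. A site that follows it would record the Day 0 count on a treated head. A site that makes both examinations would hold two Day 0 findings with no rule for choosing between them.

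The secondary comparison of mean change in live lice is at stake. A count made after application has lost whatever lice the product has already killed. The calculated decline then omits that early kill, and omits it unequally if the two products act at different speeds.

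**Working it through.** The plan states no figure for this point, so there is none to reproduce. The check compares the sections and then works out the effect of a post-application baseline.

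**1. What is timed before application?**

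| Section | Day 0 item | Timing relative to application |
|---|---|---|
| 7.1 | Head Lice Visual Assessment | After, by its label |
| 7.3.1 | Examination for living lice, at least one louse, severity rating | Before: listed ahead of assignment and application |
| 4.1 | Screening and severity rating | Before |
| 4.1 | Count of live lice and nits by stage | Day 0, otherwise not stated |
| 16.1 | Head Lice Visual Assessment | Day 0, otherwise not stated |

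Eligibility and severity-based assignment cannot be done without an examination before treatment, so one exists. It needs only one louse and a rating from comb strokes, not a count. Sections 7.3.2 to 7.3.4 list the Head Lice Visual Assessment and the examination for living lice as separate items, so the screening examination in 7.3.1 cannot simply be taken to be the named assessment.

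**2. Which analyses use the baseline count?**

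- Using it: the decline in live lice (4.2.1), the mean change to Day 14 (4.2.3, 10.3, 10.4.2) and the mean change to Day 7 (10.3).
- Not using it: the primary lice-free proportion at Day 14 (4.2.2), the lice-free proportions at Day 2 and Day 7, the proportion re-treated at Day 7, and the live count at the Day 7 visit.

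**3. Effect of a post-application baseline.** Let B be the pre-treatment mean count (assumed equal in the arms), r_T and r_C the shares of lice still alive at the post-application count in the test and control arms, and E_T and E_C the Day 14 means.

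- Pre-application baseline: difference in decline = (B − E_T) − (B − E_C) = E_C − E_T.
- Post-application baseline: (r_T·B − E_T) − (r_C·B − E_C) = (E_C − E_T) + B·(r_T − r_C).

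The bias is therefore B·(r_T − r_C). It is zero when the two shares are equal, and its sign depends on which arm has more surviving lice at that moment.

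**4. Numbers, all assumed.** Take B = 100, E_T = 15 and E_C = 55. The pre-application baseline gives 55 − 15 = 40. The post-application baseline gives 40 + 100·(r_T − r_C):

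| r_T | r_C | Difference in decline |
|---|---|---|
| 0.30 | 0.30 | 40 |
| 0.05 | 0.30 | 15 |
| 0.12 | 0.55 | −3 |
| 0.30 | 0.90 | −20 |
| 0.05 | 0.90 | −45 |
| 0.90 | 0.30 | 100 |

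The first five rows assume that the spray leaves no more survivors than the control at that count, and they run from −45 to +40. The last row reverses that assumption and exaggerates the benefit.

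**5. The pilot figure.** Section 10.5 reports that a pilot of the spray "showed high early lice kill (88% lice free at day 0 after treatment". If that share applied to the Day 0 count here, 0.88 × 26 = 22.88 (about 23) of the 26 evaluable subjects planned for the test arm, or 0.88 × 29 = 25.52 (25 or 26) of the 29 enrolled, would have a baseline of zero and could show no decline.

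**The case against.** The strongest reply is that the label in 7.1 is loose drafting that cannot be followed literally. The same sentence would put medical history after treatment, whereas 7.3.1 takes it before eligibility is verified. The label may have been meant only for adverse events, whose reporting starts at first application (8.3), or for irritation. The count in 4.1 also shares its sentence with consent and the pregnancy test, which must come before treatment. This stands as far as it goes: a pre-treatment examination is required, and nothing suggests that anyone chose a post-treatment baseline. It does not supply a statement that the full count comes before application.

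Three stronger readings are tempting, and the documents do not support them.

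- A reader might infer that the plan has no usable baseline and that its change analyses are already lost. The harm is conditional on the literal reading of 7.1 and on that count being used as the baseline.
- A reader might project the pilot's 88% onto the test arm. Section 10.5 does not say how long after application the pilot assessment was made. In this trial the spray stays in for at least 8 hours and is washed out at home (4.1, 6.1.5, 6.1.8), so an on-site count after application would normally fall during exposure. There is no matching figure for permethrin, so a reversal of the comparison cannot be claimed either.
- A reader might infer that irritation analyses are harmed too. No planned analysis uses change from baseline in irritation. Tolerability rests on itching and stinging/burning scores at follow-up visits (Synopsis, 7.1.1), safety reporting is descriptive (10.4.3), and scalp condition is judged at entry through the exclusion criteria.

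**Conclusion.** The point holds as an internal inconsistency combined with a missing definition. Section 7.1 conflicts with 7.3.1 and 4.1 on when the Day 0 louse assessment takes place, no section places the full live-louse count before application, and Section 10 does not define baseline.

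The exposure is limited to the secondary change-in-count analyses at Day 7 and Day 14. It arises only if the site follows 7.1 as written and the resulting count is used as baseline. In that case the bias is the pre-treatment mean times the between-arm difference in surviving share, assuming equal pre-treatment means. The documents give none of these quantities, so its size and direction stay open, and the figures in the working only illustrate how wide the range could be. The primary endpoint and the other lice-free proportions are unaffected.

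It is worth correcting because a pre-application count that was never recorded cannot be recovered at analysis.

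**What to change.** Four edits:

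1. In 7.1, remove the post-treatment label from the Head Lice Visual Assessment, so that the section agrees with 4.1 and 7.3.1.
2. In 7.3.1, state that the full count of live adults and nymphs is made and recorded at the examination before application.
3. In 10.4.2, define baseline as the last full live-louse count (adults plus nymphs) before the first application on Day 0, and apply it to both the Day 7 and the Day 14 changes.
4. If any Day 0 check after application is wanted, list it as a separate item in 7.1 and in the schedule of events, so that it cannot be taken for the baseline.

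The cost is small but not purely editorial. The pre-treatment examination, already set at 15 minutes or more, must yield a full count and not only presence and severity, so screening may take somewhat longer. Sample size, endpoints and tests do not change.

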7.1.1. Study specific procedures

In addition to the regular standard of clinical care, the following study specific procedures will be included as part of the study.

- Past medical history of and previous treatment of head lice must be recorded irrespective of the term it was given. Corresponding condition shall be captured in the subject's Medical History.
- Visual Assessment of Head Lice:
Subjects and their household members will be thoroughly assessed for the presence or absence of live head lice, including adult lice, nymphs, and nits. Results will be recorded on Source Document.
- Skin/Scalp Irritation Assessment:
Subjects will be assessed for skin and scalp pruritus, erythema, excoriation, and pyoderma. Results will be recorded on the Source Document.
- Ocular Irritation:
Subjects will be assessed for eye irritation, conjunctivitis, and ocular hyperemia. Results will be recorded on the Source Document.
- Subject Household Instructions:
Administration of a checklist for rinse/ shampoo time and date; and daily laundry and disinfection measures will be collected at all follow-up visits.
- Subject Assessments:
Administration of questionnaire for subject-reported outcomes. The site will complete a Subject Self-Assessment Worksheet to record the grading of Itching and Stinging/Burning sensations. Analysis of tolerability will be based on a 7 point scoring scale of Stinging/Burning and Itching sensations collected during Subject Self-Assessment at all follow-up visits.

7.2 Laboratory procedures and evaluations

7.2.1 Clinical laboratory evaluations

A urine pregnancy test will be performed for females of childbearing potential, this includes all female subjects. The baseline result must be available and must be negative before each female subject can receive study drug. A positive pregnancy test will disqualify the entire household from participation in the study.

7.3 Study schedule

7.3.1 Screening/randomization

Screening Visit Day 0 (Visit 1)

- Obtain informed consent of potential participant verified by signature on written informed consent.
- Record demographic information, obtain medical history, and history of head lice.
- Review medications history and concomitant/prohibited medications to determine eligibility
- Verify inclusion/exclusion criteria.
- Collect urine sample for pregnancy testing for all subjects of childbearing potential.
- Perform assessment for living head lice on subjects and household members for a minimum of 15 minutes. Each subject must have at least 1 live louse. Rate severity of infestation. After each subject has been identified, additional infested household members will also be assessed for infestation.
- Level of infestation will be rated as heavy, moderate or light described by how quickly lice were found during combing: heavy infestation = >1 louse with one stroke of the comb; moderate infestation = 1 louse with one stroke of the comb; light infestation = first louse found only after several strokes of the comb
- Household members must have an active head lice infestation defined as: At least 1 live lice (adult and/or nymph) present on the scalp and/or hair, as determined by a trained evaluator. Household members will be assigned to the same study group as index case.
- Schedule study visits for participants who are eligible and available for the duration of the study.
- Randomly assign subjects to treatment or control group based on infestation severity alternation system (i.e., randomly assign pairs of equal severity levels to treatment and control groups, a form of stratified random sampling) to achieve balanced representation of severity in the two groups.
- Investigational Product Dispensation/ Application for subject.
- Provide each subject with homecare instructions including combing after first wash out.
- Inform subject when to come back for each follow-up visit.
- Provide Standard of Care treatment on-site to unqualified infested household members.

7.3.2 Follow up

Follow-up Visit (Day 2) Visit 2 (+24hrs.)

- Medical History, Vital Signs, Physical Examination, Head Lice Visual Assessment, Local Skin/Scalp Irritation, Assessment, Ocular Irritation Assessment. Record results on Source Document.
- Record adverse events as reported by participant or observed by investigator.
- Record subject's adherence to homecare instructions.
- Perform assessment for living head lice on subject for visual confirmation of infestation.
- Record subject's adherence to homecare instructions.
- Inform each subject when to come back for their visit (Day 7) Visit 3 ± 1 days

